## Assessment for LTBI treatment phase

#### Evaluation at central location

Participants who have a positive TST or who report symptoms of TB will be asked to have:

 A chest Xray in a mobile x-ray van located at central location, in or near their village. Images will be exported to our online data repository. Images will either be read by an onsite radiologist or initially assessed using a validated artificial intelligence program for detection of TB. In the latter case, those images flagged as abnormal will be re-read by an onsite radiologist (see "Chest radiograph report form"). Chest xrays will be classified by each reader as: "consistent with TB", "abnormality, other than TB" and "normal or no significant abnormality". Women who state they are pregnant or attempting to fall pregnant will be excluded from chest radiography.

2. Baseline measurement of body weight, blood pressure and blood tests for liver function tests (LFT), full blood count (FBC). The physical examination findings will be recorded on the "Body weight, Blood Pressure forms".

# *Further assessment of pregnant women, those attempting to fall pregnant and those who are breastfeeding*

Women who say they are pregnant or who say they are attempting to fall pregnant will not be referred for chest radiograph or for consideration for treatment of LTBI. However, if they meet the symptom or TST criteria for screening for active TB, they will be asked to provide a single sputum specimen for Xpert testing, as described above.

Women who are breastfeeding, but who are not currently pregnant or trying to become pregnant, will be referred for chest radiograph and counselled about their risk of TB. However, they will not be considered for treatment of LTBI.

# *Further assessment of participants with abnormal chest xray or with positive sputum Xpert tests*

Those with chest Xray reported as "consistent with TB" or with any Xpert MTB positive sputums will be asked to produce two further sputum specimens for sputum microscopy, mycobacterial culture, and drug susceptibility testing (see "Sputum culture form"). Those participants whose sputum sample tests positive for Xpert MTB and/or have sputum mycobacterial cultures reported as positive for *M. tuberculosis* (on antigen testing) will be notified and referred to a central location for further evaluation. If TB diagnosis is confirmed, standardized TB treatment will be provided to the patients by the National TB Programme in accordance with policy. The outcome of the evaluation and the decision on TB treatment will be recorded.

No person who has a chest Xray reported as "consistent with TB" will be considered eligible for treatment of LTBI unless and until they have two sputum mycobacterial cultures reported as negative for *M. tuberculosis*.

Those with chest xray reported as "abnormality, other than TB" will be referred for clinical evaluation at the Provincial TB Program, or elsewhere, at the discretion of the study medical officer.

[figure not shown]

Figure 2: Flow chart of assessment for active TB

#### TB preventive treatment in those with LTBI but without active TB

Participants who meet **all** of the following criteria will be eligible for treatment for LTBI:

- Are aged  $\geq$  5 years and have consented to the screening phase; AND
- Have a TST  $\geq$  10 mm (and are not known to be HIV +ve); AND
- Are not excluded from 3HP regimen by the pregnancy or lactation screening questionnaire; AND
- Have not completed a course of treatment for TB within the preceding two years; AND
- Do not have a history of allergy or known hypersensitivity to any of the study drugs; AND
- Do not have active TB according to the following criteria:
  - 1. Expectorated sputum tested negative for MTB on GeneXpert or did not produce a sputum specimen for Xpert testing **AND** have a chest x-ray that was not reported as "consistent with TB" **OR**.
  - 2. Did not have a chest radiograph **BUT** have two sputum specimens that both tested negative for MTB on GenXpert **OR**
  - 3. Have a chest x-ray that was reported as "consistent with TB" **BUT** have two sputum cultures that have been reported as negative for TB and any GeneXpert tests (if collected) are negative for TB.

will be recommended for further assessment for treatment of LTBI by field worker.

#### Informed consent for treatment for LTBI

If eligible for treatment, according to the above criteria, participants will be provided with a written and oral explanation of the rationale for treatment (see "PIS2 – Treat" / "PCF2 – Treat") (see page 33). Written informed consent for participation in the LTBI treatment phase of the study will be sought.

#### Check criteria

If one or more the following criteria are met, participants will be reviewed by a doctor prior to treatment:

- Have symptoms of extrapulmonary TB (neck swelling or weight loss)
- Are noted to be taking any regular medications.
- Report allergy to rifampicin, rifapentine or isoniazid
- Report known liver disease or hepatitis
- Have baseline transaminases that are abnormal
- Have baseline Hb, WCC or plts that are outside the laboratory normal range
- Respond positively to any of the symptoms on the checklist for screening prior to each treatment administration
- Currently (in the last month) drink more than 14 standard drinks of alcohol per week for men and 7 standard of alcohol per week for women

will be flagged for review by the trial doctor prior to TB preventive treatment. If they do not meet any of the preceding check criteria they proceed directly to treatment without medical review.

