## Limitations of existing approaches and of some alternatives

The long-standing dominant global strategy for TB control has enhanced passive case finding and treatment at its core. This strategy focuses on improving access to TB diagnosis, treatment and care to ensure that patients who have TB disease are diagnosed and treated appropriately when they present with symptoms of TB. Although there have been substantial gains in TB control in some rapidly developing, middle income countries (particularly in China) (4), the decline in incidence of TB has been exceedingly slow in many high TB burden countries and the prevalence remains very high (5\*), ensuring ongoing transmission of TB infection. Barriers to the implementation of the current strategy include health system weakness, particularly in primary care (6), and the fact that many patients with pulmonary TB do not report typical or diagnostic symptoms (5\*) or delay seeking treatment due to the indolent nature of the disease and due to social stigma (7). As a consequence, a significant proportion of new TB patients (2.9 million in 2019 (1)) are not diagnosed and treated. Although economic development and health system strengthening will lead to a decline in TB burden in many countries (6), at the present rate of progress this will take many decades (3). Consequently, the high burden of TB will continue, with little progress towards targets, despite substantial ongoing investment in TB control programs (8).

Considerable resources and hopes have been invested in the development of new drugs, to shorten the duration of treatment, and new vaccines to prevent infection, progression or reactivation (3). Sadly, while new drugs have been developed for management of TB that is resistant to the existing first- and second-line drugs, the much anticipated blockbuster drugs for drug-susceptible TB and vaccines (9) have not eventuated and will not arrive in time to achieve these targets.

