#### Medical Review

The study doctor will conduct a medical review prior to commencing TB preventive treatment (see "Medical assessment – baseline") for eligible participants who meet one or more criteria, defined as above

The objectives of the medical review are as follows.

- 1. To resolve any medical issues that require resolution as a result of the checks (symptom screen and blood tests) performed at baseline. If this cannot be done based on the information available at the time of the initial assessment, it is expected that the trial doctor will refer the patient to an appropriate clinic or other medical facility. If the participant has an acute illness (unrelated to TB) at the time of medical review, LTBI treatment may be delayed for up to 8 weeks from that date. If the patient's symptoms persist after 8 weeks, the participant will not be eligible for treatment of LTBI in the current phase.
- 2. Decide, in consultation with the participant, whether the participant should receive treatment for LTBI. Among the relevant considerations are the following:
  - a. Participants who have significant liver function abnormalities defined as an AST or ALT level greater than or equal to three times higher than the

Upper Limit of Normal (ULN) will not be offered treatment. They will be offered referral to a liver clinic.

- b. Participants who are regularly taking medications that interact with rifamycins, where the interactions cannot easily be managed, will not be offered treatment (see Appendix to Manual of Procedures).
- c. If, as a result of this assessment, it is apparent that the participant has another severe or life-threatening illness, he or she will not be offered treatment for LTBI. This will be at the discretion of the trial medical officer.
- 3. If it is decided that the participant should receive treatment for LTBI, define whether he or she is in the low- or high-risk monitoring for adverse events below).

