#### Symptom screening

The participant will be interviewed using the "Symptom Screening prior to Administering Medications questionnaire. This may be completed by phone or face-toface interview. If the participant responds positively to any of the symptoms on the checklist, the Adverse event management procedure will be implemented and a the eCRF "Adverse events" form will be submitted within 24 hours (even if unsure about whether it is an adverse event). If the Treatment Officer is unsure about whether a participant has had an Adverse Event, or whether Active TB should be investigated, he/she should discuss with the Medical Advisor by telephone.

If the participant has experienced any of the symptoms on the Symptom Screening checklist, do NOT dispense medication unless and until instructed to do so by Medical Advisor.

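### A chest film read as consistent with TB is not a trigger for doctor review before 3HP, so some culture-negative participants start treatment without a doctor weighing that reading (minor, cheap to improve)

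*Protocol*

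**What the plan says.** **Eligibility.** Three places in the protocol agree: criterion 3 of the LTBI treatment-phase eligibility list (section 7), the section on further assessment of abnormal films (section 8), and the third route in the section on TB preventive treatment. A film read as consistent with TB bars 3HP until the cultures are back. The third route then admits a person who has "two sputum cultures that have been reported as negative for TB and any GeneXpert tests (if collected) are negative for TB".

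**Review before treatment.** The Check criteria section lists eight triggers: symptoms of extrapulmonary TB, regular medication, allergy to the study drugs, known liver disease, abnormal transaminases, abnormal blood counts, a positive pre-dose symptom checklist, and alcohol intake. For everyone else: "If they do not meet any of the preceding check criteria they proceed directly to treatment without medical review".

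**Content of the review.** The first objective under Medical Review is to resolve issues arising as a "result of the checks (symptom screen and blood tests) performed at baseline". The second is to decide, with the participant, whether to treat. Its list opens with "Among the relevant considerations are the following", so it is not exhaustive.

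**Other films.** A film showing an abnormality other than TB leads to a different step: the person "will be referred for clinical evaluation at the Provincial TB Program, or elsewhere, at the discretion of the study medical officer".

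**The concern.** The trigger list sends a mildly abnormal blood count or any regular medication to a doctor, but not a film suggestive of TB. Negative cultures make active pulmonary TB less likely without excluding it. If such a person did have culture-negative active TB, they would start the two-drug weekly regimen of section 9 instead of the standard treatment under Study setting and population (four drugs for two months, then three for four months).

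Later safeguards exist. When the pre-dose screen is positive, staff must "do NOT dispense medication unless and until instructed to do so by Medical Advisor", and a TB diagnosis ends 3HP. Both depend on symptoms or on a diagnosis being made, and the protocol's Background says that "many patients with pulmonary TB do not report typical or diagnostic symptoms". What is at stake is individual safety, not the primary comparison.

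**Working it through.** There is no plan figure to reproduce. The check is a trace of the written pathway, followed by a rough size for the cost of the fix.

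**Trace, from film to first dose**

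1. The TST is 10 mm or more, so a chest film is requested (Evaluation at central location). A radiologist reads it, or re-reads it after an artificial-intelligence flag: consistent with TB.
2. Two further sputum specimens are cultured. Both are negative, and so is any Xpert.
3. The participant is eligible by the third route. A field worker recommends further assessment and consent is sought.
4. Check criteria: none of the eight triggers concerns the film. The explicit TB-symptom trigger covers neck swelling and weight loss. Whether cough is caught depends on the pre-dose checklist, whose items the protocol does not list.
5. With no trigger met, treatment starts. A Treatment Officer dispenses, and the Medical Advisor is involved only if symptoms are reported or the officer is unsure.

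No step requires a doctor to weigh the film against the cultures. In the eligibility list, the attending medical officer's judgement concerns drug interactions and severe illness, not the film.

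**How many would be reviewed anyway**

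One trigger is wide: "Have baseline Hb, WCC or plts that are outside the laboratory normal range". Section 10 gives haemoglobin as 12.9–14.2 g/dL, a window of 14.2 − 12.9 = 1.3 g/dL. Assume haemoglobin is normal with its mean at mid-window, 13.55 g/dL, where escape from the trigger is most likely. Then P(within) = 2Φ(0.65/SD) − 1:

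| Assumed SD (g/dL) | Share within window |
|---|---|
| 1.0 | 0.484 |
| 1.5 | 0.335 |
| 2.0 | 0.255 |

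These shares are illustrative. The mean and SD are not in the protocol, and the printed row may be unreliable: its limits have a ratio of 14.2/12.9 = 1.10, against 53.7/37.7 = 1.42 for haematocrit in the same table.

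**Extra reviews if the film became a trigger (adults)**

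Inputs: 104 intervention clusters and 720 eligible participants per cluster (Sample size), or about 1,000 adults (Cluster selection); 80% screened (the modelling assumption in section 2); 38% with latent infection (section 2, taken as TST-positive); 1–5% of films read as consistent with TB (assumed).

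- At 720 per cluster: 104 × 720 × 0.80 × 0.38 = 22,764 films; 1% = 227.6 and 5% = 1,138.2.
  - Low: 227.6 × 0.255 = 58, or 0.6 per cluster.
  - High: 1,138.2 × 0.484 = 551, or 5.3 per cluster.
- At 1,000 per cluster: 104 × 1,000 × 0.80 × 0.38 = 31,616 films; 5% = 1,580.8.
  - High: 1,580.8 × 0.484 = 765, or 7.4 per cluster.

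These figures still include people barred by a positive culture or Xpert, people without two cultures, and people caught by other triggers. They leave out children. If the haemoglobin trigger caught nobody, the same chain would give 720 × 0.80 × 0.38 × 0.01 = 2.2 to 1,000 × 0.80 × 0.38 × 0.05 = 15.2 per cluster.

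**The case against.** The strongest reply is that the steps were divided on purpose. Pulmonary TB is settled before consent, by the film, Xpert and two cultures. The check list comes afterwards and covers drug safety and what sputum cannot exclude, which would explain why its TB item is extrapulmonary. On this view a second look at the film either changes nothing or overrides the culture rule without a criterion. The missing Figure 2, the baseline medical assessment form and the Manual of Procedures might also contain the step.

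Much of this stands. The sequence is coherent, the culture rule is demanding, and nothing in the text contradicts itself. The override argument does not stand: Medical Review already lets the doctor decide on treatment from an open list of considerations, so weighing the film fits an existing role. The unseen material could supply the step, but it would then disagree with the explicit closing sentence of the check list.

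A reader might infer that nobody qualified looks at the film. The protocol does not support that, because a radiologist reads or re-reads it. A reader might also take the referral of films with a non-TB abnormality as proof that the less suspicious film is handled more carefully. That contrast is weak. Those films get no culture work-up from the film reading, so referral is their diagnostic route, and the first eligibility route admits those people to 3HP without making the referral a precondition.

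**Conclusion.** The point holds as a minor patient-safety improvement. On the written text, a participant with a film read as consistent with TB, two negative cultures, any Xpert negative and none of the eight triggers starts 3HP without a doctor weighing that film in the treatment decision. One who is reviewed for another reason has a doctor who may consider the film but is not directed to it.

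Neither the number on this path nor the number with culture-negative active TB can be derived from the protocol. The 25–48% who might escape the haemoglobin trigger is conditional on an assumed distribution and a possibly unreliable reference row, so it should not be quoted as a bound. A reader might go on to infer that active TB is being knowingly undertreated or that the primary result is biased; the documents support neither.

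**What to change.** 1. In Check criteria, add a trigger: *Have a chest X-ray reported as consistent with TB*.
2. In Medical Review, objective 1, change the bracketed list of baseline checks to *symptom screen, chest X-ray and blood tests*, so that a review prompted by anything else also takes in the film.
3. Leave the two-negative-culture rule as it is. If Figure 2 or the baseline medical assessment form already contains this step, bring the text into line with it.

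The cost is two wording changes, an unknown but probably small number of extra reviews by study doctors already in post (roughly 0.6 to 7 adults per cluster under the stated assumptions), and a short delay to 3HP for people who have already waited for culture results.

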#### Medical Review

The study doctor will conduct a medical review prior to commencing TB preventive treatment (see "Medical assessment – baseline") for eligible participants who meet one or more criteria, defined as above

The objectives of the medical review are as follows.

- 1. To resolve any medical issues that require resolution as a result of the checks (symptom screen and blood tests) performed at baseline. If this cannot be done based on the information available at the time of the initial assessment, it is expected that the trial doctor will refer the patient to an appropriate clinic or other medical facility. If the participant has an acute illness (unrelated to TB) at the time of medical review, LTBI treatment may be delayed for up to 8 weeks from that date. If the patient's symptoms persist after 8 weeks, the participant will not be eligible for treatment of LTBI in the current phase.
- 2. Decide, in consultation with the participant, whether the participant should receive treatment for LTBI. Among the relevant considerations are the following:
  - a. Participants who have significant liver function abnormalities defined as an AST or ALT level greater than or equal to three times higher than the

Upper Limit of Normal (ULN) will not be offered treatment. They will be offered referral to a liver clinic.

- b. Participants who are regularly taking medications that interact with rifamycins, where the interactions cannot easily be managed, will not be offered treatment (see Appendix to Manual of Procedures).
- c. If, as a result of this assessment, it is apparent that the participant has another severe or life-threatening illness, he or she will not be offered treatment for LTBI. This will be at the discretion of the trial medical officer.
- 3. If it is decided that the participant should receive treatment for LTBI, define whether he or she is in the low- or high-risk monitoring for adverse events below).

#### Monitoring for adverse events

Participants who meet one or more of the following criteria

- aged  $\geq$  45 years,
- have baseline AST or ALT higher than normal (but less than three times the upper limit of normal), OR
- are flagged by the trial doctor for the high-risk monitoring for adverse event

will have liver function tests repeated at two weeks, at four weeks after commencement of treatment and then at four weekly intervals throughout treatment.

#### Follow-up during the TB preventive treatment period

At the first visit a Treatment Officer, together with a member of the commune health staff assigned by the commune health post/ap coordinator, will visit study participants in individual to:

- Confirm name of participant ID (matching PID, names, age and photograph)
- Provide participant screening results
- Obtain written informed consent for treatment of LTBI.

At each follow-up visit during treatment, the treatment team will evaluate the participant for the presence of adverse events and dispense medications, as described below.

#### Participant identification

The visit may be conducted at the household or at the Ap central office, depending upon the requirements of the participant.

A Treatment Officer, together with a member of the commune health staff assigned by the commune health post/ap coordinator, will visit study participants to confirm the identity of the participant (matching PID, names, age and photograph).

#### Symptom screening

The participant will be interviewed using the "Symptom Screening prior to Administering Medications questionnaire. This may be completed by phone or face-toface interview. If the participant responds positively to any of the symptoms on the checklist, the Adverse event management procedure will be implemented and a the eCRF "Adverse events" form will be submitted within 24 hours (even if unsure about whether it is an adverse event). If the Treatment Officer is unsure about whether a participant has had an Adverse Event, or whether Active TB should be investigated, he/she should discuss with the Medical Advisor by telephone.

If the participant has experienced any of the symptoms on the Symptom Screening checklist, do NOT dispense medication unless and until instructed to do so by Medical Advisor.

#### Dispense medication

If

- The identity of the participant has been confirmed using matching of their PID, names, age and photograph, AND
- "Symptom screening prior to administering treatment" is negative or the Medical Advisor has authorised dispensing medication

then give the study participant one package of one week of medication (1 dose of 3HP) and record the following information in the eCRF

- Directly Observed Therapy (DOT) or Self-administered therapy (SAT) method
- date of delivery,
- package number,
- PID,
- signature of person receiving the medication,
- signature of the Treatment Officer (see MOP- Supply Chain and Pharmacy Management)

If DOT method is implemented, observe participant swallowing the medication and record that this has been observed in the "Drug Dispensing- Field worker".

